1. Collect and review the phone/visit log (these are the same questions asked during the weekly phone call) and exercise log to see what the participant did during the past weeks, discuss barriers, successes, and problem solve if needed. Participants can return logs either in person, over email or by text.
2. Collect and review the protein tracker to ensure that the participant is consuming adequate protein to build lean mass through resistance exercise. Participants can return logs either in person, over email or by text.
3. Visually evaluate the participant's ability to increase weight and adjust the amount of weight appropriately.

In between Exercise Sessions and after the initial 4-6 Sessions, the exercise professional will contact each participant 1 time per week either by phone or video and ask a series of questions

(see Appendix 13.5.5). These calls may be completed through the centralized calling center, by an exercise professional from one of the three study sites. Questions will assess adherence of the patient to the exercise regimen and the pattern of sessions with regard to time between sessions; protein supplement adherence; and any medical complications that prevented exercise sessions from occurring. A contact card will be mailed to participants when they are halfway through the intervention.

Table 6. Intervention Contacts

What	Number of times*	Aim	Time per session
Pre-In Person Training Visit Phone Call	1 time prior to 1 st Exercise Session	Make introductions, orient participant to intervention, obtain health information on participant	20-30 min
Exercise Sessions	4-6 times, every 2-3 weeks during first 3 months of intervention	Learn and progress with exercise protocol	60 min
Home Exercise Sessions	2 times per week	Resistance exercise	45 min
Log Exercise	At-home exercise sessions	Log adherence	5 min
Log Protein Intake	Daily	Log adherence	5 min
Phone or Video Call	Weekly	Track adherence	5 min
Contact Card	1 time	Encourage participation, remind participants to return logs	n/a

*Each cycle is administered every 2-3 weeks

1. The exercise professional will speak with participants to review these exercise and protein logs each week, by phone or video conference, until the intervention is complete at approximately 6 months post initiation (corresponding to completion of adjuvant chemotherapy).

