4. STUDY MEASUREMENTS

Initial screening will take place via telephone. At the in-person baseline visit, after the patient signs the consent form, s/he will undergo a series of baseline assessments, questionnaires and blood draws as described above. Many of the data collection instruments will be either data entered by a researcher or self-administered by participants into REDCap, which is a secure web application for managing online surveys and databases. The table below provides an overview of the measurements that participants will undergo over the course of the protocol and the timing of these measurements:

Table 7. Measurement Schedule

Measure	Screening	Baseline	Weekly	PK Cohort Only	Post-Intervention Visit ³
Phone screening questions- PA screening and additional questions	X				
PAR-Q	X				
SF-36 ⁴		X			X
Demographics ⁴		X			
Paffenbarger questionnaire		X			X
Physical function tests (balance, gait speed, sit and stand, grip strength)		X			X
Food frequency questionnaire ⁴		X			X
Height, weight, waist and hip circumference		X			X
Whole body DXA		X		X ²	X
Patient-completed side effects questionnaires ⁴		X			X
D3- creatine dilution		X			X
NCI PRO CTCAE			X ¹		
Medical record review for chemotherapy dosing and toxicities			X		
Physical activity and nutrition logs			X		
Inflammatory markers		X			X
Pharmacokinetics (PK)				See section 4.14	
Injury history questionnaire ⁴					X
Intervention follow-up survey					X

¹ At each scheduled intervention visit (for intervention arm) and thereafter by phone or secure web-link every time chemotherapy appointment is scheduled. For U group controls, an RA will administer by phone or secure web-link every time a chemotherapy appointment is scheduled.

² For PK cohort, a DXA scan will also occur at time of 2nd PK draw, at approximately 4 months after initiation of the intervention

³ To be conducted within 2 weeks after last cycle of chemotherapy and end of intervention

⁴ As a result of COVID-19, to reduce in person time participants will complete baseline and post-intervention questionnaires virtually. Study staff will email participants a secure web-link, send them home with paper copies to be mailed back within 3 days, or administer questionnaires over the phone.

4.1 Screening questionnaire:

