At the initiation of adjuvant chemotherapy, we will ascertain planned treatment course for participants, including planned cumulative dose and planned treatment duration. We will then examine the EMR for changes in chemotherapy dose and timing. The following variables will be defined for each drug administered:

- Planned dose intensity (mg/week) = planned total dose / planned duration of therapy (weeks)
- Actual dose intensity (mg/week) = actual total dose (mg) / actual duration of therapy (weeks)
- Relative dose intensity (RDI) (%) = actual total dose intensity / planned total dose intensity
- Average relative dose intensity (ARDI) (%) = the average across all regimens of the relative dose intensity
- Number of cycles of chemotherapy and date of initiation of each cycle

In addition, we will report on early stoppage by calculating actual number of cycles / planned number of cycles of adjuvant therapy. We will only consider dose reductions that occur after start of intervention. Chemotherapy treatment forms will be used to capture data from the EMR on chemotherapy administration (see Appendix 13.7.4). A researcher will record all relevant chemotherapy treatment variables in an online REDCap form.

4.12 Chemotoxicity:

Total combined number of moderate and severe chemotherapy-associated toxicities, assessed via medical record review, patient-completed NCI PRO-CTCAE and patient-completed side effects questionnaires. As shown in the Appendix, we will use a series of validated questionnaires for chemotherapy-associated side effects including NCI PRO-CTCAE and a questionnaire on neurotoxicity utilized in a recent phase III trial with oxaliplatin⁴⁸. See Appendix 13.7. Throughout the intervention, the research manager or assistant will email a secure web-link to the patient requesting completion of the NCI PRO-CTCAE questionnaire in advance of his/her next chemotherapy infusion visit. A researcher will record all relevant chemotoxicity variables in an online REDCap form. Participants will complete the patient-completed side effects questionnaire and NCI PRO-CTCAE questionnaire in online REDCap surveys.

4.13 Inflammatory blood measures:

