### **1.2 Chemotherapy-associated toxicities**

We will examine differences in chemotherapy tolerance through patient-reported outcomes. The NCI Patient-Reported Outcomes-Common Terminology Criteria for Adverse Events (PRO-CTCAE) is a patient-reported outcome measurement system developed to characterize the frequency, severity, and interference of symptomatic treatment toxicities. Participants completed a customized 9-item PRO-CTCAE questionnaire around the initiation of each chemotherapy cycle reporting on the following symptomatic toxicities: nausea, vomiting, diarrhea, shortness of breath, hand-foot syndrome, numbness in hands and feet, pain, muscle aches and fatigue. Each symptom had 1-3 questions that asked about frequency and/or severity, and/or interference. Answers from those questions were then categorized as none, mild, moderate, or severe, based on expert consensus of oncologists [1].

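### Table 7 footnote 1 collects the PRO-CTCAE differently by arm during the exercise-session phase and conflicts with Protocol 4.12 and SAP 1.2, so the SAP's toxicity analyses are open to a bias of unknown direction

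*Protocol*

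**What the plan says.** Four places describe when and how the PRO-CTCAE is completed.

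- **Protocol Table 7, footnote 1, RT arm:** "At each scheduled intervention visit (for intervention arm) and thereafter by phone or secure web-link every time chemotherapy appointment is scheduled".
- **Protocol Table 7, footnote 1, controls:** "For U group controls, an RA will administer by phone or secure web-link every time a chemotherapy appointment is scheduled". Table 7 itself places the item in its weekly column.
- **Protocol 4.12:** research staff "will email a secure web-link to the patient requesting completion of the NCI PRO-CTCAE questionnaire in advance of his/her next chemotherapy infusion visit". No arm is named.
- **SAP 1.2:** "Participants completed a customized 9-item PRO-CTCAE questionnaire around the initiation of each chemotherapy cycle". Again no arm is named.

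Protocol Table 6 gives the timing of the exercise sessions: "4-6 times, every 2-3 weeks during first 3 months of intervention". Section 3.8 intends them to fall on infusion days as far as that can be arranged. It also makes sessions 2-6 virtual after COVID-19.

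On sources of toxicity data, Protocol 4.12 has toxicities "assessed via medical record review, patient-completed NCI PRO-CTCAE and patient-completed side effects questionnaires". SAP 1.2 is narrower: "We will examine differences in chemotherapy tolerance through patient-reported outcomes". All three toxicity analyses in SAP 2.2 (A, B and C) use the patient's own ratings.

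**The concern.** Toxicity is a primary endpoint, it is self-reported, and patients know whether they are training. In that situation the collection procedure should be identical in the two arms. Footnote 1 makes it differ in setting (exercise visit or not), mode (visit against phone or web-link) and trigger (exercise schedule against chemotherapy appointment). Any effect of these on reporting would be counted as a treatment effect.

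Two mechanisms are possible, and they need not act in the same direction. Patients may rate symptoms differently at an exercise visit than on a web-link. And if sessions and cycles do not line up, RT patients may report more or fewer times, or on different cycle days. Analyses A and B ask whether a symptom was ever moderate or severe, so each further report can only raise the result. The available SAP text makes no allowance for the number of reports. Analysis C works per cycle and depends less on the number, but that text does not say which report counts when a cycle contains two.

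**Working it through.** **The plan's own figure.** The documents give no number of PRO-CTCAE reports per arm. The nearest figure is the detectable difference of 0.42 SD for RDI and toxicity counts (Protocol 9.3.4). It reproduces: 90 per arm gives t-test power 0.800, and 0.42 × 17.3 = 7.27, stated as 7.3%. It is not in dispute here.

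**How long the split lasts.** Footnote 1 moves RT patients to phone or web-link at chemotherapy appointments after the intervention visits, as for controls. The difference therefore covers the 4-6 sessions of the first 3 months. Protocol Table 3 includes 3-month FOLFOX (6 cycles of 14 days) and 3-month CAPOX (4 cycles of 21 days). For these patients the session phase can cover most or all of treatment.

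**Whether the number of reports differs.** Over 12 weeks, two-weekly sessions give 12/2 = 6 and three-weekly sessions give 12/3 = 4. These equal the 6 FOLFOX and 4 CAPOX cycles in Table 3. If sessions follow the patient's own cycle, the comparison is 6 against 6 or 4 against 4. Alignment is only an aim, however, and nothing fixes the session count by regimen.

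**What unequal numbers would do.** Assume k independent reports, the same risk p per report in both arms, and no true effect. Neither p nor independence comes from the documents. The chance that a given symptom is ever reported as moderate or severe is 1 − (1 − p)^k.

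At p = 0.10:
- 4 reports: 1 − 0.9^4 = 34.4%, or 8 × 0.344 = 2.75 of 8 symptoms.
- 6 reports: 1 − 0.9^6 = 46.9%, or 8 × 0.469 = 3.75 of 8 symptoms.

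Ratios, RT to control:

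| Reports, RT vs control | p = 0.02 | p = 0.05 | p = 0.10 | p = 0.20 |
|---|---|---|---|---|
| 6 vs 6 (aligned) | 1.00 | 1.00 | 1.00 | 1.00 |
| 4 vs 6 | 0.68 | 0.70 | 0.73 | 0.80 |
| 6 vs 4 | 1.47 | 1.43 | 1.36 | 1.25 |
| 10 vs 12 | 0.85 | 0.87 | 0.91 | 0.96 |

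The last row is 6-month FOLFOX with 4 sessions in place of the first 6 reports (4 + 6 = 10 against 12). For analysis A's composite of 8 symptoms, also taken as independent, the chance of any is 1 − (1 − p)^(8k). At p = 0.02 this is 47.6% for 4 reports and 62.1% for 6, an odds ratio of 0.56, or 1.80 if the arms are exchanged.

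**Mode and setting.** These can act even when numbers are equal. If RT reports at exercise visits were 10% lower (an assumed figure), analysis C would show a rate ratio of 0.90 for a patient whose whole treatment falls in that phase. With 6 of 12 cycles affected and a constant rate per cycle, it would show (6 × 0.90 + 6 × 1.00)/12 = 0.95.

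**The case against.** A reader might infer from footnote 1 that the number of reports differs by arm. The documents do not show this. Sessions are meant to coincide with infusions, the 4-6 count matches the cycle count of each 3-month regimen, and regimen is both a minimization factor and a model covariate. A comparison of 6 sessions with 4 CAPOX cycles puts a FOLFOX rhythm against a CAPOX control. Repeated reports from one patient are also probably positively correlated, which would bring the ratios above closer to 1. This objection stands: an unequal number is possible, not established.

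A reader might also infer that RT patients report symptoms to their own trainer. Footnote 1 does not say who administers the questionnaire at those visits. The tasks listed for follow-up sessions in Protocol 3.8 do not include it, and Protocol 4.12 has participants complete it online. Nor does the footnote make the difference last for the whole trial.

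Nor can it be inferred that controls go unreported when chemotherapy is delayed. Their trigger is a scheduled appointment, not a dose given.

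Finally, SAP 1.2 already describes collection per cycle without regard to arm, which may be what was done. RDI, the other primary endpoint, comes from the medical record and is not affected. None of this removes the conflict: footnote 1 remains in the protocol and prescribes a split that the other two passages do not.

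**Conclusion.** The point holds in limited form. It is certain that footnote 1 prescribes arm-specific setting, mode and trigger during the exercise-session phase, and that this conflicts with Protocol 4.12 and SAP 1.2. It follows that analyses A, B and C can be biased, because the trial is unblinded and the available SAP text has no other toxicity measure.

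Direction and size are unknown. With aligned sessions, the bias from the number of reports is nil. Under the assumed range p = 0.02 to 0.20 with independent reports, a mismatch of 4 against 6 gives ever-reported ratios of 0.68 to 0.80, and the reverse mismatch gives 1.25 to 1.47. These are illustrations of sensitivity, not estimates for this trial. An effect of mode or setting could remain even with equal numbers, and nothing in the documents allows it to be quantified.

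**What to change.** **Protocol.** Replace footnote 1 with the Protocol 4.12 procedure in both arms: a self-completed web-link, sent by research staff in the same window before each cycle start, with a research assistant's phone call as the fallback in both arms, and not at exercise sessions. Tie the window to cycle start and not to infusion, because oral capecitabine has no infusion.

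**SAP.** State how the questionnaire was in fact collected in each arm. For A, B and C, use one report per chemotherapy cycle: the one nearest cycle start within the same window in both arms. Tabulate the number, timing and mode of reports by arm.

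**Data already collected.** SAP 2.1 reports 183 participants randomized, so a change to the footnote may come too late for many or all of them. Apply the one-report-per-cycle rule to the existing data. If the number of reports still differs by arm, add a sensitivity analysis restricted to the same cycles in both arms. Do not simply delete reports taken at exercise sessions, since that removes RT data only. On 12-cycle FOLFOX it could leave 6 RT reports against 12. At p = 0.10 in the model above, that is 46.9% against 71.8%, a ratio of 0.65 with no true effect.

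**Cost.** Wording in two documents and one table. The web-link and the research staff are already in place. Off-window and duplicate reports drop out of the main analysis.

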9.2	Sample size, accrual time and study duration:	30
9.3	Statistical analysis:.....	31
10.	STUDY INVESTIGATORS	32
11.	DATA PRIVACY AND SECURITY	32
12.	REFERENCE LIST	34
13.	APPENDIX	38
13.1	Recruitment Communications	38
13.2	Phone Screening Forms and Questionnaires.....	38
13.3	Consent Form	38
13.4	Baseline and Post-Intervention Questionnaires.....	38
13.5	Physical Activity Assessments and Exercise Intervention Materials	38
13.6	Nutrition Assessments and Intervention Materials.....	38
13.7	Chemotherapy Toxicity, Side Effects, and Injury History Forms and Email.....	38
13.8	Anthropometric Measurements and Blood Draw Procedures	38
13.9	Usual Care Handout	38
13.10	Thank You Card Text.....	38

PROTOCOL SUMMARY

Protocol Version Date: 2/11/2022

Principal Investigators: Multiple PI: [name] DrPH, Kaiser Permanente of Northern California (Corresponding PI); [name], Pennsylvania State University; [name], Dana-Farber Cancer Institute

PROTOCOL TITLE

1. Full Title: FORCE: Focus on Reducing Dose-Limiting Toxicities in Colon Cancer with Resistance Exercise

STUDY SPONSORSHIP

- 1. Funding Sponsor:** NATIONAL CANCER INSTITUTE/NIH
- 2. Primary Sponsor:** Kaiser Permanente of Northern California – [name]

PROTOCOL ABSTRACT

FORCE is a randomized home-based resistance training/strength training (RT) intervention study for Stage II and III colon cancer patients undergoing chemotherapy.

Participants will be 180 newly diagnosed Stage II and III colon cancer patients from Kaiser Permanente of Northern California (KPNC), the Penn State Cancer Institute (PSCI), and the Dana Farber Cancer Institute (DFCI). The intervention will begin by the third visit for adjuvant chemotherapy and continue exercise through the completion of post-operative chemotherapy. Specifically, we will examine between group differences for RT versus waitlist control for chemotherapy outcomes including dose delays, dose reductions, early stoppage and Grade 3 and 4 toxicities. We will also study changes in muscle mass (MM) and changes in specific inflammatory markers (e.g. CRP, IL-6 and TNF-RII) as potential markers of change in response to RT. To determine effects of change of MM on chemotherapy-specific drug clearance, we will examine the impact body composition changes on the pharmacokinetics (PK) of 5-FU and oxaliplatin, two of the most commonly used drugs for colon cancer.

OBJECTIVES

1. Primary Objective:

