Beginning in 1990, an NCI expert panel recommended 5-fluorouracil (5-FU) and leucovorin (LV) as adjuvant therapy for patients with stage III colon cancer⁵. While initial studies tested a longer duration of treatment, the current standard is 6 months of therapy. An oral form of 5-FU, called capecitabine, has also demonstrated noninferiority as an alternative to IV 5-FU⁶. Select stage II patients, based on recurrence risk, are considered for adjuvant therapy as well. Further trials demonstrated a modest, but statistically significant, benefit to adding oxaliplatin to 5-FU/LV. The most common regimen is a 3 drug infusional combination called FOLFOX (5-FU/LV and oxaliplatin), now standard treatment for most stage III patients, considered in some stage II patients⁴ as well as in stage IV/metastatic disease patients. Substitution of capecitabine for infusion 5-FU and leucovorin is another treatment regimen (CAPOX). Dosing of 5-FU/LV, capecitabine or FOLFOX is based on a standard formula that incorporates a patient’s height and weight into a metric called, body surface area (BSA)⁷. Recommended milligrams per BSA were derived from trials testing for dose limiting toxicities (DLT), typically defined as severe (grade III or IV based on the NCI Common Toxicity Criteria [CTC] scale). While a standard starting dose is defined for each treatment option, many patients will still derive significant toxicities (Table 1). Issues with BSA dosing include the use of absolute weight without consideration of body composition or physiologic measures relevant for drug metabolism and disposition, such as renal and hepatic function. **Dosing based on BSA is limited in ability to reduce inter-patient variability in a drug’s volume of distribution⁸.** Various drug elimination processes (e.g. metabolic breakdown or excretion) account for inter-patient variability in pharmacokinetics to a large degree⁸. Body composition (i.e. adipose tissue and muscle mass)⁹ is another factor influencing pharmacokinetics and may predict toxic reactions to certain chemotherapy regimens^{10;11}.

Table 1. Select Toxicities associated with adjuvant therapy⁴

Toxicity	5-FU/LV		FOLFOX	
	Any Grade	Grade 3/4	Any Grade	Grade 3/4
Neutropenia	40%	5%	79%	41%
Low platelets	19%	<1%	77%	2%
Nausea	61%	2%	74%	5%
Diarrhea	48%	7%	56%	11%
Neuropathy	16%	<1%	92%	12%

1.3 Toxicities of adjuvant therapy:

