2. OBJECTIVE

2.1 Primary Objective:

To examine differences in dose reductions, dose delays and early stoppage for chemotherapy and the total combined number of moderate and severe chemotherapy-associated toxicities between intervention group and waitlist controls.

2.2 Secondary Objectives:

2.2.1 Examine specific inflammatory markers (CRP, IL-6, TNF- α receptor II [TNF-RII]) in relation to baseline MM and FM and examine differences in changes in inflammatory markers between intervention group and waitlist controls.

2.2.2 Examine the impact of intervention versus control and RT-induced body composition changes on the pharmacokinetics [PK] of 5-FU and oxaliplatin between baseline and 4 months of RT.

2.3 d3 Creatine Objectives:

2.3.1 Test whether resistance training during chemotherapy (FORCE intervention group v. control) increases d3 creatine muscle mass at 6 months.

2.3.2 Evaluate the association of d3 creatine muscle mass with changes in functional status and strength during chemotherapy.

2.3.3 Evaluate the association of d3 creatine muscle mass with chemotherapy toxicity and relative dose intensity.

2.3.4 Evaluate the association of d3 creatine muscle mass with cancer-related biomarkers, including inflammation, CEA levels and cardiometabolic risk factors.

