- Grade 3 (severe) Events – Only events that are unexpected and possibly, probably or definitely related/associated with the intervention.

- All Grade 4 (life-threatening or disabling) events – Unless expected AND specifically listed in the protocol as not requiring reporting.
- All Grade 5 (fatal) Events – When the participant is enrolled and actively participating in the trial OR when the event occurs within 30 days of the last study intervention.

Participating investigators must report each serious adverse event to the Kaiser Permanente Overall Principal Investigator within 24 business hours of learning of the occurrence. In the event that the participating investigator does not become aware of the serious adverse event immediately (e.g., participant sought treatment elsewhere), the participating investigator is to report the event within 24 business hours after learning of it and document the time of his or her first awareness of the adverse event. Report serious adverse events by telephone, email or facsimile to:

[name]
Division of Research
Kaiser Permanente
[name]
[name]
[contact]
[contact]

Within the following 24-48 hours, the participating investigator must provide follow-up information on the serious adverse event. Follow-up information should describe whether the event has resolved or continues, if and how the event was treated, and whether the participant will continue or discontinue study participation.

6.4.4 Reporting to the Institutional Review Board (IRB):

All unanticipated serious adverse events should be reported to the Kaiser Permanente IRB as defined by the PI Reportable Event and Incident Requirements SOP KPNC-502. Other investigative sites should report serious adverse events to their respective IRB according to the local IRB's policies and procedures in reporting adverse events.

6.4.5 Reporting to Hospital Risk Management:

Participating investigators will report to their local Risk Management office any subject safety reports or sentinel events that require reporting according to institutional policy.

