9.2.1 From Section D. Study overview of the original KPNC application approved 2017

3. How many participants will be enrolled in this study, or how many electronic records or medical records will be used? Provide your best estimate if you are not sure

Number of KPNC participants or records:	Approximately 115 participants to be enrolled
Records used:	Approximately 7500-KPNC records used
Number of non-KPNC participants or records:	Approximately 65 participants enrolled
Total number of participants or records:	Approximately 180* participants enrolled

**Due to the impact of the COVID-19 pandemic on the study, we estimate that the total number of participants will be within the range of 10% above the original total of 180 participants*

9.3 Statistical analysis:

9.3.1 Primary endpoints:

All data analyses will be by intent-to-treat, though in exploratory analyses we will consider compliance to intervention (defined as $\geq 75\%$ of planned sessions) and changes in MM. We will use multiple linear regressions to assess the difference between the intervention and wait-list control groups in mean relative dose intensity (RDI) for each agent and in mean average RDI (ARDI) across all agents. Continuous model covariates will be categorized either as quartiles or into clinically relevant categories (e.g. WHO BMI classification).

Analysis of number of grade 3 and 4 toxicities in relation to randomization arm will utilize Poisson regression given that this outcome can be characterized as a count. These regression models will provide point and interval estimates of adjusted proportional differences in rates of toxicities (expressed as rate ratios) between the control and intervention groups.

9.3.2 Secondary endpoints:

Analyses of inflammatory markers in relation to baseline body composition will utilize multiple linear regression techniques. These analyses of associations at baseline will be conducted in each randomization arm separately, followed by an analysis in the full sample (differences in associations at baseline across arms are not expected).

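### The toxicity endpoint counts moderate and severe events, but the protocol's toxicity model counts only grade 3 and 4 and the SAP covers only PRO-CTCAE symptoms, so moderate toxicities in the medical record are in no specified between-arm analysis

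*Protocol*

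**What the plan says.** **Endpoint.** The primary objective (protocol 2.1) concerns "the total combined number of moderate and severe chemotherapy-associated toxicities between intervention group and waitlist controls". Section 4.12 defines the measure as "Total combined number of moderate and severe chemotherapy-associated toxicities, assessed via medical record review", and adds the PRO-CTCAE and patient-completed side effects questionnaires as further sources.

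**Protocol analysis.** The abstract lists the chemotherapy outcomes as "dose delays, dose reductions, early stoppage and Grade 3 and 4 toxicities". Section 9.3.1 says: "Analysis of number of grade 3 and 4 toxicities in relation to randomization arm will utilize Poisson regression". The protocol contains no other between-arm toxicity model.

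**Grade labels.** Section 6.4.3 has entries for "Grade 3 (severe) Events" and for "All Grade 4 (life-threatening or disabling) events". Section 1.2 describes dose-limiting toxicities as "typically defined as severe (grade III or IV based on the NCI Common Toxicity Criteria" scale).

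**SAP.** Section 1.2 uses a nine-item PRO-CTCAE: "Answers from those questions were then categorized as none, mild, moderate, or severe". Section 2.2 leaves out muscle aches and compares the arms on the other eight symptoms in three ways:
- A: any symptom moderate or severe (logistic regression);
- B: the number of symptoms, 0 to 8, that were moderate or severe at least once (Poisson with overdispersion);
- C: the number per cycle (Poisson GEE).

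The SAP has no grade 3-4 analysis and no analysis of toxicities from the record or the side effects questionnaire.

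**Power (9.3.4).** Power is .80 for .42 SD in a two-sided t-test, stated to cover both RDI and the number of toxicities.

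**The concern.** Moderate and severe is not the same set of events as grade 3 and 4 when grade 3 is already called severe. The model in 9.3.1, run as written, would count a rarer set of events than the one the primary objective names. The SAP restores the severity range but narrows the source to patient-reported symptoms, and neither document explains either change.

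Two things are at stake. First, the medical record is the first source that 4.12 names, and its moderate events enter no planned comparison. Second, with two thresholds and several sources in the current texts, a reader of the results cannot tell which toxicity count was meant to be primary. That leaves room for the choice to be made after the data are seen.

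**Working it through.** **1. Threshold**

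| Place | What is counted |
|---|---|
| Protocol 2.1 and 4.12 | moderate and severe |
| Protocol abstract and 9.3.1 | grade 3 and 4 |
| Protocol 6.4.3 (labels) | grade 3 is severe; grade 4 is life-threatening or disabling |
| SAP 2.2 | moderate or severe, PRO-CTCAE only |

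On the protocol's own labels moderate lies below grade 3, so the 9.3.1 model excludes it.

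**2. Source**

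| Source in 4.12 | Between-arm analysis of moderate events |
|---|---|
| PRO-CTCAE | yes, SAP 2.2 A, B and C |
| Medical record | none (9.3.1 stops at grade 3-4; SAP silent) |
| Side effects questionnaire | none specified |

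Neutropenia and low platelets are not PRO-CTCAE items in SAP 1.2. In protocol Table 1 (FOLFOX) they contribute .41 + .02 = 0.43 grade 3/4 toxicities per patient and .79 + .77 = 1.56 of any grade. The lower-grade remainder is 1.56 − 0.43 = 1.13 per patient. Some unknown share of that is moderate.

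**3. The plan's own figure**

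With 90 per arm, the normal approximation gives (1.960 + 0.842) × √(2/90) = 0.418 SD. The exact t calculation gives 0.420 SD, with power .800 at .42. The figure reproduces. It is in SD units, so it does not change with the grade threshold.

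**4. Rate-ratio scale (illustration)**

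Inputs from Table 1, FOLFOX, five listed toxicities:
- grade 3/4: .41 + .02 + .05 + .11 + .12 = 0.71 per patient;
- any grade: .79 + .77 + .74 + .56 + .92 = 3.78 per patient.

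The documents give no moderate rate. Assumed moderate-plus-severe means therefore run from 1.02 to 3. The lowest supposes that one tenth of the lower-grade events are moderate: 0.71 + 0.10 × (3.78 − 0.71) = 1.02.

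With control mean μ, rate ratio RR and variance φ times the mean, SE(log RR) = √[φ/(90μ) + φ/(90μ·RR)], and power = Φ(|log RR|/SE − 1.96). For RR = 0.75, |log RR| = 0.288. At μ = 0.71 and φ = 1, SE = √(1/63.9 + 1/47.9) = 0.191, and power = Φ(1.51 − 1.96) = .32.

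| Control mean | Power, φ = 1 | Power, φ = 1.5 |
|---|---|---|
| 0.71 (grade 3-4) | .32 | .23 |
| 1.02 (assumed) | .44 | .31 |
| 1.5 (assumed) | .59 | .43 |
| 2 (assumed) | .71 | .54 |
| 3 (assumed) | .87 | .71 |

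With φ = 1, the grade 3-4 count gives up about 26%, 45%, 55% and 63% of the power available at means 1.02, 1.5, 2 and 3. It reaches .80 at RR = 0.56, a reduction of about 44%.

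**The case against.** The strongest reply is that the SAP has already settled the matter. It is the later text: it reports 183 randomised participants and describes questionnaire completion in the past tense. It analyses moderate or severe toxicity in three ways and contains no grade 3-4 count. This largely stands. A reader of the protocol alone might infer that every moderate toxicity is left out of the planned analyses, and the SAP shows that this is not so. What the reply does not reach is the record. The SAP does not say that the record-based part of 4.12 has been dropped, or that 9.3.1 is superseded.

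A reader might also infer that most of the power is lost. The documents do not support that:
- The .42 SD statement is untouched.
- The loss on the rate-ratio scale depends on a moderate rate that is not given. At assumed means of 1.02 and 1.5 it is under half.
- The calculation supposes the same rate ratio for moderate and severe events, uses five selected toxicities, and uses FOLFOX only. The 5-FU/LV grade 3/4 rates sum to only about 0.14 to 0.16, depending on whether the entries below 1% are taken as 0 or 1%.

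Nor do the documents show that the detectable effect is implausibly large. At mean 0.71, .42 SD is a reduction of about 44% with the two arms' Poisson variances averaged, or 50% with the control SD alone. The nearest effect in the protocol, dose adjustments in Table 2 (9/76 against 26/77), is a 65% relative reduction, though for a different endpoint in breast cancer.

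Finally, 2.1 and 4.12 never equate moderate with a particular CTCAE grade, so a grade cut-off cannot simply be read into them.

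**Conclusion.** The inconsistency is real, concerns a primary endpoint and should be corrected. It needs no assumption: the protocol's objective and endpoint definition include moderate toxicities, its toxicity model excludes them, and the SAP brings them back only for eight patient-reported symptoms. Moderate toxicities in the medical record, haematological ones among them, are left without a specified between-arm comparison.

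The cost in power is only illustrative. For a 25% reduction it is about .32 with a grade 3-4 count, against .44 to .87 for assumed moderate-plus-severe means of 1.0 to 3 (Poisson, 90 per arm, equal rate ratios across grades). The documents cannot place the trial within that range.

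**What to change.** 1. In the protocol abstract and 9.3.1, replace the grade 3 and 4 count by moderate and severe, in line with 2.1, 4.12 and the SAP.
2. In the SAP, name analysis B as the patient-reported toxicity analysis.
3. Add to the SAP a separate record-based count of moderate and severe toxicities, with each toxicity counted once per patient, using the same overdispersed Poisson model and randomisation covariates. State explicitly which CTCAE grades count as moderate and as severe.
4. Keep the grade 3-4 count as a supportive analysis.
5. Do not merge the record and PRO-CTCAE into one count. The PRO-CTCAE categories come from a composite of patient answers and are not CTCAE grades.
6. State what role, if any, the side effects questionnaire has in the endpoint.

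The cost is mainly text, since 4.12 already plans the record review. One point cannot be confirmed: the toxicity abstraction form (Appendix 13.7.5) is listed by title only, so the grades it captures are not visible. If it omits moderate events, records would have to be abstracted again. The other drawback is that moderate events may be charted less completely than severe ones, which is the reason to keep the grade 3-4 count alongside.
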